3.9. Safety Analysis

3.9.1. Adverse Events

Adverse events will be coded by System Organ Class and Preferred Term using the Medical Dictionary for Regulatory Activities (MedDRA[®]) Version 19.0 or higher. The verbatim term will be included in the AE listings.

An AE (classified by preferred term) will be considered as treatment-emergent AE (TEAE) if the event is newly occurring or worsening on or after the date of first dose of study drug.

The number and percentage of subjects reporting TEAEs in each treatment group during the double-blind period will be presented by treatment group for the following categories:

- System organ class and preferred term
- Preferred terms in decreasing frequency, and also including the following subsets:
 - Experienced by $\geq 2\%$ of subjects in any treatment group
 - Experienced by $\geq 5\%$ of subjects in any treatment group and ≥ 2 times of placebo group
- System organ class, preferred term, and severity
- System organ class, preferred term for severe TEAEs
- System organ class, preferred term, and relationship
- System organ class, preferred term for drug-related TEAEs

If more than one AE is coded to the same preferred term for the same subject, the subject will be counted only once for that preferred term using the most severe and most related occurrence for the summarization by severity and by relationship to study drug.

In addition, the number and percentage of subjects reporting AEs during the Safety Follow-up Period will be tabulated by the system organ class, preferred term and treatment group.

The number and percentage of subjects who have serious adverse events (SAE) and AEs leading to premature discontinuation from the treatment will be summarized by preferred term and treatment group and will be sorted by decreasing frequency for ALKS 3831 group.

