## 7. SELECTION AND WITHDRAWAL OF SUBJECTS

### 7.1. Subject Inclusion Criteria

Each subject must meet all of the following inclusion criteria to be qualified to participate in this study.

1. Is willing and able to provide written informed consent
2. Is age 18–70 years, inclusive, at screening
3. Has a body mass index (BMI) of 18.0–40.0 kg/m^2, inclusive at screening
4. Agrees to abide by the contraception requirements specified in the protocol
5. Meets criteria for the DSM-5 diagnosis of schizophrenia, confirmed with the Mini International Neuropsychiatric Interview (MINI):
  - Is currently experiencing an acute exacerbation or relapse
  - If inpatient at screening, has been hospitalized for less than two weeks for the current exacerbation
6. Total PANSS Score  $\geq$ 80 at screening and baseline (Visits 1 and 2)
7. A score  $\geq$ 4 on at least three of the following PANSS Positive Scale (P) Items at Visits 1 and 2:
  - Item 1 (P1; delusions)
  - Item 2 (P2; conceptual disorganization)
  - Item 3 (P3; hallucinatory behavior)
  - Item 6 (P6; suspiciousness/persecution)
8. CGI-S Score  $\geq$ 4 at screening and Visits 1 and 2
9. Resides in a stable living situation when not hospitalized
10. Subjects at some sites may be required to have an informant or caregiver who meets some or all of the following criteria in accordance with the locally approved informed consent form (ICF):
  - a. Informant or caregiver will be in contact with the subject several times per week
  - b. If necessary, the informant or caregiver will accompany the subject to visits
  - c. Informant or caregiver will help ensure maximum subject adherence to study procedures
  - d. The informant or caregiver must be willing and able to provide informed consent by signing the caregiver ICF.
11. Is willing and able to provide government-issued identification

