## 8. STUDY DESIGN

### 8.1. Overall Study Design and Plan

This is a Phase 3, multinational, multicenter, randomized, double-blind, placebo-controlled study in subjects experiencing an acute exacerbation of schizophrenia. Subjects will be screened up to 10 days prior to randomization. Upon completion of screening assessments, subjects meeting eligibility criteria will be admitted to an inpatient unit on Day -1, if they are not already inpatient. Currently prescribed antipsychotics will be discontinued at screening.

Study design and timeline are summarized in the schematic shown in [Figure 1](#).

On Day 1 (Visit 2), subjects meeting eligibility criteria will be randomized in a 1:1:1 fashion to one of the following 3 treatment groups: ALKS 3831, olanzapine, or placebo, and will receive double-blind treatment for up to 4 weeks.

On Days 1 and 2, subjects randomized to ALKS 3831 will receive 10/10 [10 mg olanzapine/10 mg samidorphan] and subjects randomized to olanzapine will receive 10 mg. On Day 3, the dose will be increased to 20/10 [20 mg olanzapine/10 mg samidorphan] for subjects randomized to ALKS 3831 or 20 mg for subjects randomized to olanzapine. Following the increase on Day 3, the dose may be decreased to 10/10 (ALKS 3831) or 10 mg (olanzapine) at end of week 1 (Day 7) or week 2 (Day 15) if there are tolerability problems based on judgment of the investigator. No further dose adjustments will be allowed Day 15 onward for the remaining 2-weeks of the treatment period. All subjects will receive 1 capsule daily in a blinded manner.

Subjects are required to be inpatient for the first 2 weeks of the treatment period (until Day 15). Following the mandatory 2-week inpatient stay, subjects can either continue the study as inpatients for the full 4-week treatment period or be discharged at the end of Week 2 or end of Week 3 if they meet the discharge criteria specified in [Section 8.1.1](#).

[figure not shown]
Following discharge, subjects will be contacted by study staff at least once between their weekly site visits to monitor their status and determine if there are any safety concerns that would precipitate re-admission to the inpatient facility. If subjects are re-admitted to the inpatient facility due to safety concerns, it will be recorded as an SAE.

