**Figure 1: Study Design Schematic**

### 8.1.1. Discharge Criteria

Subjects are eligible to be discharged at end of Week 2, Week 3, or Week 4 if they meet ALL of the following criteria:

1. Subjects are judged clinically suitable for discharge by the investigator:
  - a. Subjects have shown a sustained pattern of improvement relative to their condition on Day 1 within the past week.
  - b. Subjects are not a danger to themselves or others
  - c. Subjects can be discharged into a supervised living environment deemed suitable by the investigator.
2. Subjects show stabilization of symptoms as confirmed by PANSS:
  - a. PANSS total score <70
  - b. Score <4 on selected PANSS positive items (Item 1 [P1; delusions], item 2 [P2; conceptual disorganization], item 3 [P3; hallucinatory behavior], and item 6 [P6; suspiciousness/persecution])
3. Subjects answer “No” on items 4 or 5 of the Columbia-Suicide Severity Rating Scale (C-SSRS-ideation), and “No” to all 5 items of (C-SSRS-behavior)

Subjects not meeting the discharge criteria will continue as inpatients for the remainder of the study and for up to 1 additional week if they do not meet discharge criteria at EOT.

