#### 13.2. Definition of Serious Adverse Event

An SAE is any AE, occurring at any dose and regardless of causality that meets one or more of the following criteria:

- Results in death
- Is life-threatening. The subject is at immediate risk of death from the reaction as it occurs. This does not include reaction that, had it occurred in a more severe form, might have caused death

- Requires inpatient hospitalization or prolongation of existing hospitalization. Hospital admission for elective surgery scheduled prior to study entry is not considered an SAE
- Results in disability/incapacity (eg, a substantial disruption of a person's ability to conduct normal life functions)
- Is a congenital anomaly/birth defect

Important medical events that may not result in death, be immediately life threatening, or require hospitalization may be considered to be SAEs when, based upon appropriate medical judgment, they may jeopardize the patient or subject and may require intervention to prevent one of the other outcomes listed above.

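### Only discharged subjects can have a re-admission SAE, and discharge depends on response, so SAE percentages by arm in SAP 3.9.1 are not directly comparable without discharge status

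*SAP*

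**What the plan says.** SAP 3.9.1 plans one SAE display: "The number and percentage of subjects who have serious adverse events (SAE) and AEs leading to premature discontinuation", by preferred term and treatment group. It has no split by inpatient or discharged status. The disposition summary in SAP 3.3 has no row for discharge from the unit.

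Protocol 8.1 keeps every subject on the ward until Day 15. After that, "subjects can either continue the study as inpatients for the full 4-week treatment period or be discharged" at the end of Week 2 or Week 3. Protocol 8.1.1 sets the conditions: "Subjects are eligible to be discharged at end of Week 2, Week 3, or Week 4 if they meet ALL of the following criteria". They include sustained improvement, "PANSS total score <70", scores below 4 on P1, P2, P3 and P6, and C-SSRS conditions. Entry requires a PANSS total of at least 80 (Protocol 7.1), so a subject discharged under these criteria has fallen by more than 10 points. Subjects who do not meet the criteria stay on the ward.

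For those who leave, Protocol 8.1 adds: "If subjects are re-admitted to the inpatient facility due to safety concerns, it will be recorded as an SAE". The general definition in Protocol 13.2 includes an event that "Requires inpatient hospitalization or prolongation of existing hospitalization", along with death, life threat, disability, congenital anomaly and important medical events.

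**The concern.** The opportunity for one kind of SAE depends on a state reached after randomisation, and that state is defined largely on the primary endpoint's scale. If ALKS 3831 and olanzapine work, more of their subjects should qualify for discharge and so become able to generate a re-admission SAE. A placebo subject who stays on the ward and worsens to the same degree cannot generate it.

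The two routes also differ in how firm they are. Recording a re-admission for safety concerns is mandatory. Calling a ward deterioration an important medical event is a matter of medical judgment under Protocol 13.2.

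Safety and tolerability is the only secondary objective. In a four-week trial an SAE table may turn on a few subjects, and the planned tables would not let a reader see how many were at risk of this event in each arm. The protocol already treats the two settings as different for another measure: Protocol 8.3.9.2.3 limits the MOAS to inpatients so that observation and rating stay consistent.

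**Working it through.** **1. The plan's own figures.** The documents state no discharge, re-admission or SAE rate. The usable design figures are in SAP Section 2: 130 per arm, a 10-point difference, SD 20 and 30% dropout. They are consistent with each other. Evaluable per arm = 130 × 0.70 = 91; SE = 20 × √(2/91) = 2.965; 10/2.965 = 3.373; power = Φ(3.373 − 1.960) = 92.1%, which meets the stated 90%. That figure is not in dispute; the 10 points and the SD are borrowed below.

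**2. Who can have a re-admission SAE.**

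| Period and setting | Re-admission SAE (Protocol 8.1) | Other Protocol 13.2 criteria |
|---|---|---|
| To Day 15, all on ward | Not possible | Open |
| After Day 15, still on ward | Not possible | Open, partly by judgment; status of a continued stay not stated |
| After Day 15, discharged | Recorded if due to safety concerns | Open |

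**3. Size of the at-risk set.** Assumptions, not in the documents: baseline mean 90 to 100; placebo mean change −10 to −20; drug 10 points better; SD 20; Week 4 values standing in for Days 15 and 22; PANSS total criterion only. Then P(PANSS <70) = Φ((69.5 − mean)/20).

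| Baseline, placebo change | Placebo | Drug | Ratio |
|---|---|---|---|
| 100, −10 | Φ(−1.025) = 15.3% | Φ(−0.525) = 30.0% | 1.96 |
| 95, −15 | Φ(−0.525) = 30.0% | Φ(−0.025) = 49.0% | 1.63 |
| 90, −20 | Φ(−0.025) = 49.0% | Φ(0.475) = 68.3% | 1.39 |

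Actual discharge would be less frequent, because the other criteria must also be met and discharge is optional. The direction is what matters: the set is larger on drug, here by a factor of 1.4 to 2.0.

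**4. From the at-risk set to the SAE percentage.** With d the share discharged, r the re-admission risk after discharge and o the percentage with other SAEs (taken as not overlapping), SAE % = d × r + o. All values of d, r and o are assumed.

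| d, placebo v drug | r, placebo v drug | o, placebo v drug | SAE %, placebo v drug | Subjects of 130 |
|---|---|---|---|---|
| 15% v 30% | 5% v 5% | 0 v 0 | 0.75 v 1.50 | 1.0 v 2.0 |
| 23% v 40% | 5% v 5% | 0 v 0 | 1.15 v 2.00 | 1.5 v 2.6 |
| 15% v 30% | 10% v 5% | 0 v 0 | 1.50 v 1.50 | 2.0 v 2.0 |
| 15% v 30% | 15% v 5% | 0 v 0 | 2.25 v 1.50 | 2.9 v 2.0 |
| 15% v 30% | 5% v 5% | 3% v 1% | 3.75 v 2.50 | 4.9 v 3.3 |

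**5. A higher assumed risk.** Take a weekly risk h over 1.5 outpatient weeks, equal in both arms, so r = 1 − (1 − h)^1.5. For h = 5%, r = 7.4%; for h = 10%, r = 14.6%. With 15% v 30% discharged, this gives 1.1% v 2.2% and 2.2% v 4.4%, or 1.4 v 2.9 and 2.9 v 5.7 subjects of 130.

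**6. Break-even.** Re-admission SAEs are equal between arms when r(placebo)/r(drug) = d(drug)/d(placebo). Over the grid in step 3, a post-discharge risk 1.4 to 2.0 times higher on placebo cancels the larger at-risk set, and anything beyond that reverses it.

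**The case against.** Much of the opposing case stands.

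- **The rate is not determined by the at-risk set.** An effective drug may well lower the risk of re-admission after discharge, and steps 4 and 6 show that a plausible difference removes or reverses the effect.
- **Ward subjects can have SAEs.** A reader might infer that worsening on the ward goes uncounted as serious. The text does not say so: life-threatening events, prolonged hospitalisation and important medical events all remain open. What is missing is a statement of how ward deterioration, or a stay continued because discharge criteria are unmet, relates to prolongation.
- **Discharge under the protocol is not the only way off the ward.** Early terminators are asked to complete safety follow-up (Protocol 7.3), and SAE collection runs to Visit 7 (Protocol 13.4). A subject who withdraws for lack of efficacy and is later hospitalised meets the Protocol 13.2 criterion. That route may load on placebo, and 30% dropout is assumed.
- **Worsening is visible elsewhere.** The SAP tabulates TEAEs by severity, AEs leading to discontinuation, reasons for discontinuation, and PANSS and CGI-S by visit. No SAE test is planned, and the mock tables are in a separate document.

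None of this makes the re-admission component comparable between arms. The other tables do not show how many subjects were discharged or for how long, so a reader cannot judge whether a small SAE difference reflects risk or opportunity.

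**Conclusion.** The point holds as one of comparability. Ascertainment of one SAE component depends on discharge, discharge depends on response, and the planned table does not show it. Re-admission SAEs, and total SAE percentages containing them, should not be compared between arms without discharge status.

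A reader might go further and infer that the SAE percentage must rise with response to drug, or that it doubles with no true difference. The documents do not support either. Only the at-risk set is expected to grow. The doubling needs a discharge ratio of 2.0, the extreme of the range in step 3, together with equal post-discharge risk, which nothing in the documents establishes.

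Under the assumed rates, re-admission SAEs involve about 1 to 6 subjects of 130 per arm, and the difference runs from about 3 more on drug to 1 more on placebo. The sign and size of any net bias cannot be fixed in advance. This is a low-cost improvement to a descriptive safety table; it does not affect the primary analysis.

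**What to change.** Keep the reporting rule and the overall SAE table. Add to SAP 3.9.1 a descriptive split by arm:

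- (a) subjects with SAEs, leaving out events that are serious solely because of re-admission after protocol discharge, as a percentage of the Safety Population;
- (b) re-admission SAEs as a count, shown with the number discharged at Day 15 or Day 22 and the outpatient weeks, with numerator and outpatient time covering the same period.

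Discharge is a scheduled item in Protocol Table 1 and re-admissions for safety concerns are already SAE records, so the cost is one extra block of rows and a flag for re-admission-only events. There are two limits. Row (b) rests on a subset formed after randomisation and is descriptive only. Row (a) may still contain hospitalisations after early termination.

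Separately, the sponsor should reconcile Protocol 8.1, 8.1.1 and 13.2, so that sites classify in the same way a deterioration on the ward and a stay continued because discharge criteria are not met. If some sites treat such a stay as prolongation and others do not, row (a) will carry that inconsistency.

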3.9.1.1. Other significant AEs

In addition, incidence of a selected subset of relevant AEs in this class of drugs (eg, extrapyramidal symptoms (EPS) TEAEs, AEs associated with abuse potential, AEs associated with drug withdrawal, and suicide related events, etc.) will be summarized by treatment group and preferred term. The selection of AEs per subset will be based on the preferred term and Standardized MedDRA queries (SMQs).

3.9.2. Clinical Laboratory Parameters

Laboratory parameters will be presented in conventional (ie, US) units. Only scheduled laboratory parameters will be included in the summaries. All laboratory data, including those collected at unscheduled visits, will be included in the listings.

Laboratory results (baseline and change from baseline) for the Safety population for chemistry and hematology parameters will be summarized by treatment group and by visit.

Number (percentage) of subjects with potentially clinically significant (PCS) values at any post-baseline visit, will be summarized by treatment group. PCS criteria are presented in [Table 1](#). The denominator is all subjects with non-PCS baseline and at least one post-baseline assessment in the Safety Population and the numerator is the number of subjects with non-PCS baseline and PCS at post-baseline. All PCS values including baseline PCS values will be included in supportive listings.

Shift tables for selected metabolic parameters (glucose, total cholesterol, LDL, HDL, tryglyceride, and HbA1c) and liver function tests will be presented. The criteria are summarized in [Table 2](#), [Table 3](#) and [Table 4](#).

Table 1: Criteria of Potentially Clinically Significant (PCS) Abnormality for Selected Analytes

Parameters	Criteria
Chemistry	
Albumin	<2.5 g/dL
Alkaline Phosphatase (U/L)	$\geq 3 \times \text{ULN}$
Alanine Aminotransferase (U/L)	$\geq 3 \times \text{ULN}$
Aspartate Aminotransferase (U/L)	$\geq 3 \times \text{ULN}$
Bilirubin, Total	$\geq 2.0 \text{ mg/dL}$
Blood Urea Nitrogen	>30 mg/dL
Cholesterol, Random	>300 mg/dL
Cholesterol, Fasting	$\geq 240 \text{ mg/dL}$
Cholesterol, HDL Fasting	$\leq 30 \text{ mg/dL}$
Cholesterol, LDL Fasting	$\geq 160 \text{ mg/dL}$
Creatine Kinase (U/L)	$\geq 3 \times \text{ULN}$
Creatinine	$\geq 2.0 \text{ mg/dL}$
Glucose, Random	<50 mg/dL or $\geq 200 \text{ mg/dL}$
Glucose, Fasting	<50 mg/dL or $\geq 126 \text{ mg/dL}$
Potassium	<3 mmol/L or >5.5 mmol/L
Lactate Dehydrogenase (U/L)	$> 3 \times \text{ULN}$
Prolactin (Female)	>30 ng/mL
Prolactin (Male)	>20 ng/mL
Sodium	<130 mmol/L or >150 mmol/L
Triglycerides, Fasting (Female)	$\geq 120 \text{ mg/dL}$
Triglycerides, Fasting (Male)	$\geq 160 \text{ mg/dL}$

Table 1: Criteria of Potentially Clinically Significant (PCS) Abnormality for Selected Analytes (Continued)

Parameters	Criteria
Hematology	
Eosinophils	$>1.0 \times 10^3/\mu\text{L}$
Hematocrit (Female)	$\leq 32\%$
Hematocrit (Male)	$\leq 37\%$
Neutrophils, Absolute	$<1.5 \times 10^3/\mu\text{L}$
Platelets	$<75.0 \times 10^3 \text{ cells}/\mu\text{L}$ or $\geq 700.0 \times 10^3 \text{ cells}/\mu\text{L}$
Leukocytes	$\leq 2.8 \times 10^3/\mu\text{L}$ or $\geq 16.0 \times 10^3/\mu\text{L}$

Table 2: Shifts Category from Baseline to Any Post-Baseline for Selected Lipid Parameters

Total cholesterol (fasting) mg/dL
Normal (<200) to high (≥ 240)
Borderline (≥ 200 and < 240) to high (≥ 240)
Normal/Borderline (<240) to high (≥ 240)
Normal (<200) to borderline/high (≥ 200)
Increase ≥ 40 mg/dL
LDL Cholesterol (fasting) mg/dL
Normal (<100) to high (≥ 160)
Borderline (≥ 100 and <160) to high (≥ 160)
Normal/borderline (<160) to high (≥ 160)
Normal (<100) to borderline/high (≥ 100)
Increase ≥ 30 mg/dL
HDL Cholesterol (fasting) mg/dL
Normal (≥ 40) to low (<40)
Decrease ≥ 20 mg/dL
Triglycerides (fasting) mg/dL
Normal (<150) to high (≥ 200)
Normal (<150) to very high (≥ 500)
Borderline (≥ 150 and <200) to high (≥ 200)

Borderline (≥ 150 and < 200) to very high (≥ 500)
Normal/borderline (< 200) to high (≥ 200)
Normal/borderline (< 200) to very high (≥ 500)
Normal (< 150) to borderline/high/very high (≥ 150)
Increase ≥ 50 mg/dL

Table 3: Shift Category from Baseline to Any Post-Baseline in Glucose and HbA1c

Serum glucose (fasting) mg/dL
Normal (< 100) to high (≥ 126)
Impaired (≥ 100 and < 126) to high (≥ 126)
Normal/Impaired (< 126) to high (≥ 126)
Increase ≥ 10 mg/dL
HbA1c %
Shift from baseline ($< 5.7\%$) to post-baseline $\geq 5.7\%$
Shift from baseline ($< 5.7\%$) to post-baseline $\geq 5.7\%$ and $< 6.5\%$
Shift from baseline ($< 5.7\%$) to post-baseline $\geq 6.5\%$

Table 4: Shift Category from Baseline to Any Post-Baseline in Liver Function Test

Alanine Aminotransferase (ALT) (U/L)
Shift from Normal to ≥ 3 x ULN
Shift from Normal to ≥ 5 x ULN
Shift from Normal to ≥ 10 x ULN
Aspartate Aminotransferase (AST) (U/L)
Shift from Normal to ≥ 3 x ULN
Shift from Normal to ≥ 5 x ULN
Shift from Normal to ≥ 10 x ULN
Bilirubin, Total (mg/dL)
Shift from Normal to > 1 xULN
Shift from Normal to ≥ 2 xULN

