#### **7.2.5. Exclusion Criteria Based on Laboratory Assessments at Screening**

20. Subject has any of the following lab results at screening:

- Hemoglobin A1c (HbA1c)  $\geq 6.0\%$
- Dyslipidemia, defined for this study as total fasting cholesterol >280 mg/dL or fasting triglycerides >500 mg/dL
- Aspartate aminotransferase (AST) or alanine aminotransferase (ALT) value  $\geq 2$  times the upper limit of the laboratory normal reference range
- Absolute neutrophil count  $\leq 1.5 \times 10^3 \mu\text{L}$
- Platelet count  $\leq 75 \times 10^3 \mu\text{L}$
- Serum creatinine >2.5 mg/dL
- Positive pregnancy test result

21. Positive serology test for hepatitis B surface antigen, hepatitis C antibody (confirmed by RNA testing), or human immunodeficiency virus (HIV) antibody at screening

22. Clinically significant ECG abnormality at Visit 1 or baseline Visit 2

23. QT interval >450 msec for men and >470 msec for women, as corrected by the Fridericia formula (QTcF), observed at Visit 1 or baseline Visit 2

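### The triglyceride shift table has no row from high (200–499 mg/dL) to very high (≥500 mg/dL), so no tabulated count identifies subjects who newly reach 500 from that band

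*SAP*

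**What the plan says.** SAP Table 2, in Section 3.9.2, sorts fasting triglycerides into normal (<150 mg/dL), borderline (150 to <200), high (≥200) and very high (≥500). Three rows end specifically in very high: "Normal (<150) to very high (≥ 500", "Borderline (≥ 150 and < 200) to very high (≥ 500" and their union, "Normal/borderline (< 200) to very high (≥ 500". A fourth row mentions the very high category but pools it with the two below: "Normal (< 150) to borderline/high/very high (≥ 150". The only triglyceride row open to every baseline is "Increase ≥ 50 mg/dL".

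Two other provisions matter:

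- **Eligibility.** Protocol Section 7.2.5 defines the excluded dyslipidemia as "total fasting cholesterol >280 mg/dL or fasting triglycerides >500 mg/dL". A screening triglyceride value of 200–499 is therefore admissible.
- **PCS count.** SAP Table 1 sets the fasting triglyceride limits at ≥120 mg/dL for women and ≥160 mg/dL for men. For the percentages, "The denominator is all subjects with non-PCS baseline and at least one post-baseline assessment in the Safety Population", and the numerator has the same baseline restriction.

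**The concern.** The step from high to very high is the shortest route into the most severe triglyceride category that the SAP defines, and it is the one step into that category without a row. To be counted as a shift to very high, a subject must go from under 200 to at least 500, a rise of more than 500/200 = 2.5-fold. A subject already at 400 who reaches 520 is not counted.

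The comparable analytes are handled differently. The pooled rows for total cholesterol (<240 to ≥240), LDL (<160 to ≥160) and, in SAP Table 3, glucose (<126 to ≥126) each run from everything below the top category into it. For triglycerides the pooled row stops at 200 although the top category begins at 500. The SAP gives no reason for this.

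At stake is the completeness of one by-arm safety count. Protocol Section 5.1 presents the combination as intended to keep olanzapine's efficacy with less weight gain and fewer associated metabolic deficits, so a reader of the study report may well look for that count.

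**Working it through.** The plan states no figure for this point, so there is nothing to reproduce. The check has two parts.

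**1. Applying the rows (documents only).** Each Table 2 triglyceride row was treated as a baseline range plus a post-baseline threshold and applied to pairs of values in mg/dL.

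| Baseline → post | Rows ending specifically in very high | Other category rows | Rise ≥50? |
|---|---|---|---|
| 120 → 520 | from normal; from normal/borderline | yes | yes (400) |
| 170 → 520 | from borderline; from normal/borderline | yes | yes (350) |
| 250 → 520 | none | none | yes (270) |
| 460 → 520 | none | none | yes (60) |
| 460 → 505 | none | none | no (45) |
| 499 → 520 | none | none | no (21) |

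Every baseline of 200–499 misses all category rows. The PCS count does not help: 200 exceeds both 120 and 160, so these subjects are already PCS at baseline and leave both numerator and denominator.

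**2. How large a share this could be (assumed inputs).** The documents give no triglyceride median, variability or expected change, so the following are assumptions:

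- lognormal values with median 100, 120 or 140 mg/dL;
- between-subject log-SD 0.4 or 0.5;
- within-subject log-SD 0.2, 0.3 or 0.4;
- on-treatment multiplier 1.0, 1.2 or 1.4, with individual log-SD 0.2 when above 1.

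That gives 3 × 2 × 3 × 3 = 54 scenarios, each simulated with 4 million subjects. Screening values above 500 and baselines of 500 or more were removed. The post-baseline value was the maximum of the two scheduled draws (Days 15 and 29, protocol Table 1).

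The quantity of interest is the share missed = (new ≥500 with baseline 200–499) / (all new ≥500).

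| Scenario group | Share missed |
|---|---|
| No drug effect | about 60% to 100% |
| 1.2–1.4-fold rise, within-subject log-SD 0.2 | 76% to 95% |
| 1.2–1.4-fold rise, within-subject log-SD 0.3 | 56% to 82% |
| 1.2–1.4-fold rise, within-subject log-SD 0.4 | 43% to 68% |

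The share is above one half in 52 of the 54 scenarios; the two exceptions are 48% and 43%. Among the missed subjects, 96% to 100% meet the row for a rise of at least 50 mg/dL.

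Expected new cases per arm of 130 (ignoring dropout) run from 0.00021 × 130 = 0.03 to 0.10917 × 130 = 14.2. A middle scenario (median 120, log-SDs 0.5 and 0.3, 1.2-fold rise) gives 0.0284 × 130 = 3.7 per arm, of which 79%, or 2.9, are in no very high row.

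With a row from 200–499 to ≥500 added, or one pooled from below 500, coverage is 100% by construction.

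**The case against.** The best defence is that the layout follows a convention. Apart from the absolute-change rows, the category rows in SAP Tables 2 to 4 start from normal, borderline or impaired baselines: liver enzymes from normal, HbA1c from below 5.7%, cholesterol from below 240. Read that way, the tables count new abnormality in subjects not already high, and the triglyceride rows do what their labels say. This stands as an explanation. It does not supply the missing count, and for cholesterol, LDL and glucose the same convention still reaches every subject below the top category.

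Two stronger readings are tempting, and the documents do not support either.

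- **That the table misses nearly all new cases.** Narrow assumptions do give 89% to 99% (median 110–130, between-subject log-SD 0.45–0.50, within-subject log-SD 0.20–0.30, a uniform rise of at most 15%). The figure depends on those choices. Allowing individual response to vary (log-SD 0.2) lowers two of those scenarios from 0.949 to 0.884 and from 0.884 to 0.822. A 30% mean rise (median 120, log-SDs 0.50 and 0.30, individual log-SD 0.2) gives 0.760.
- **That such values are hidden.** SAP Section 3.9.2 lists all laboratory data and all PCS values, including those that were PCS at baseline. The by-visit chemistry summaries include the maximum (SAP Sections 3.1 and 7), so a scheduled value of 500 or more would show there by arm. Under protocol Sections 13.1 and 18.1, out-of-range values that the investigator judges clinically significant are recorded as adverse events.

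It is also fair that this is a 4-week trial with an efficacy primary objective and a general safety secondary objective, that the lipid shifts are descriptive, and that the counts will probably be too small to separate the arms.

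**Conclusion.** The gap is real and follows from the text alone: no Table 2 row and no PCS count identifies subjects with baseline 200–499 mg/dL who newly reach 500 mg/dL. Most would appear under the rise of at least 50 mg/dL, which says nothing about crossing 500, and a few would meet no row. The individual values are still reported, so the defect is an incomplete by-arm count, not a loss of data.

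Its size cannot be derived from the documents. On the assumed inputs above, the omitted subjects are 43% to nearly 100% of new cases, probably a majority, with absolute numbers from almost none to about 9 per arm (14.2 × 0.64) at the extreme. The point is minor: it concerns a descriptive safety table and leaves the primary and key secondary analyses untouched.

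**What to change.** Add two triglyceride rows to SAP Table 2:

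- High (≥200 and <500) to very high (≥500)
- Normal/borderline/high (<500) to very high (≥500)

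For each, the denominator should be the subjects in that baseline category with at least one post-baseline value. The second row gives the complete count of new cases by arm; the first shows how many came from the adjacent category.

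The cost is two more rows in an existing table, programmed from data already collected. The only downside is that the counts may be small. No visit, sample or efficacy analysis changes.
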